4.2.7.4 Primary Analysis of Secondary Endpoint (Overall Survival)

[figure not shown]
The analysis of OS is based on the FAS. The number and percentage of participants experiencing an OS event and Kaplan-Meier plots, for dose levels with at least participants of OS may be presented. The median OS and two-sided 95% CI will be estimated using the Kaplan-Meier method (if participant numbers allow).

Summaries of the number and percentage of participants who have died, those still in survival follow-up, those lost to follow-up and those who have withdrawn consent will be provided.

A summary of the duration of follow-up for OS will be included using median (range). This will be presented for censored participants.

The proportion of participants alive at 6, 12, 18 and 24 months and associated two-sided 95% CI will be estimated using the Kaplan-Meier method.

4.2.7.5 Sensitivity Analysis of OS Endpoint

4.2.8 Other Endpoints

The analysis of the exploratory research endpoints will be handled outside this SAP and reported separately from the Clinical Study Report (CSR).

4.2.9 Pharmacodynamic Endpoint

Analysis of pharmacodynamic data will be described in a separate analysis plan.

4.3 Pharmacokinetics

This section covers details related to pharmacokinetics (PK) endpoints and analyses.

4.3.1 Serum Pharmacokinetic Concentration Data

Serum concentrations for each scheduled time-point are summarized by dose level in Part A and by cohort in Part B using appropriate descriptive statistics. Any issues considered to impact the PK data may result in the exclusion of concentration data from the PK analysis and/or exclusion of parameters and concentrations from the PK descriptive statistics and/or inferential statistical analyses, the reason(s) for exclusion(s) will be documented by the PK Scientist. These will be agreed between the PK Scientist and the AstraZeneca Clinical Pharmacology Scientist prior to the final PK analysis and handover of parameters to programming and identified in the PK flagging file and/or PK handover document. However, any excluded data will be presented in the listings.

For Part B where intensive PK sample are collected for the China population, a full set of PK NCA parameters will be provided separately from the Global and Japanese population for the final PK analysis.

The following descriptive statistics are presented for serum concentrations:

- n
- n below LLOQ
- geometric mean (gmean)
- geometric coefficient of variance (%) (gCV)
- arithmetic mean (mean)
- arithmetic standard deviation (Std Dev)
- median
- minimum (min)
- maximum (max)

The gmean is calculated as $\exp(\mu)$, where μ is the mean of the data on the natural log scale.

The gCV is calculated as 100 x sqrt[exp(s²)-1], where s is the Std Dev of the data on the natural log scale.

Where required for plots: The gSD is calculated as $exp(\sigma)$, where σ is the standard deviation of the data on the natural log scale. The gmean \pm gSD (gmean-gSD and gmean+gSD) are calculated as $exp[\mu \pm s]$.

Protocol scheduled times are used to present the PK concentration summary tables and corresponding gmean concentration-time figures.

Handling of Non-Quantifiable Concentrations

Individual concentrations below the LLOQ of the bioanalytical assay are reported as NQ in the listings with the LLOQ defined in the footnotes of the relevant TFLs. Individual serum concentrations that are Not Reportable are reported as NR and those that are missing are reported as NS (No Sample) in the listings. Serum concentrations that are NQ, NR or NS are handled as follows for the provision of descriptive statistics:

- Any values reported as NR or NS are excluded from the summary tables and corresponding figures.
- At a time point where less than or equal to 50% of the concentration values are NQ, all NQ values are set to the LLOQ, and all descriptive statistics are calculated accordingly.
- At a time point where more than 50% (but not all) of the values are NQ, the gmean and gCV% are set to Not calculable (NC). The maximum value is reported from the individual data, and the minimum and median are set to NQ.
- If all concentrations are NQ at a time point, no descriptive statistics are calculated for that time point. The gmean, minimum, median and maximum are reported as NQ and the gCV% as NC.
- The number of values below LLOQ (n < LLOQ) are reported for each time point together with the total number of collected values (n).

Three observations > LLOQ are required as a minimum for a serum concentration or PK parameter (eg, Cmax) to be summarized. Two observations > LLOQ are presented as minimum and maximum with the other summary statistics as NC.

4.3.2 Serum Pharmacokinetic Parameter Data

The pharmacokinetic (PK) parameters of the serum concentration data for sabestomig will be derived using non-compartmental methods in Phoenix® WinNonlin® Version 8.3 or higher (Certara).

PK analysis is, where data allow, carried out using actual elapsed times determined from the PK sampling and dosing times recorded in the database. If actual elapsed times are missing, nominal times may be used at the discretion of the AZ PK Scientist with approval from the

AZ Clinical Pharmacology Scientist (CPS). Nominal sampling times may be used for any agreed interim PK parameter calculations.

For each PK sampling period, serum concentrations that are non-quantifiable (NQ) from the time of pre-dose sampling (t=0) up to the time of the first quantifiable concentration is set to a value of zero. After this time point, NQ serum concentrations are set to missing for all concentration profiles. Where 2 or more consecutive concentrations are NQ at the end of a profile, the profile is deemed to have terminated and therefore any further quantifiable concentrations are set to missing for the calculation of the PK parameters unless it is considered to be a true characteristic of the profile of the drug.

If an entire concentration-time profile is NQ, the profile is excluded from the PK analysis.

Cmax, Crough, tmax, and tlast are taken directly from the concentration-time profiles.

Refer to Appendix C for the calculation of PK parameters to be estimated, where possible and appropriate, from the PK serum concentration.

PK parameter Listings

All reportable PK parameters, including individual diagnostic and lambda z related parameters, are listed for each participant, for each analyte separately.

PK parameter descriptive statistics

All primary and secondary PK parameters are summarized for each analyte by dose level in Part A and by cohort in Part B using appropriate descriptive statistics.

The descriptive statistics for PK parameters are presented as follows:

- Cmax, Ctrough, AUCinf, AUClast: present n, gmean, arithmetic mean of non logtransformed data (mean), arithmetic standard deviation (Std Dev), gCV(%), median, min and max.
- t½λz, CL, Vss, Vz: present n, arithmetic mean of non log-transformed data (mean), arithmetic standard deviation (Std Dev), median, min and max.
- Cmax/D, Ctrough/D, AUCinf/D, AUClast/D, λz: present n, gmean, gCV(%), mean, Std Dev, median, min and max.
- tmax and tlast; present n, median, min and max.
- Diagnostic parameters (eg, λz lower, λz upper, λzN, Rsq, Rsq adj, λz span ratio, and AUCextr): present n, arithmetic mean, Std Dev, gmean, gCV%, median, min and max.

Three values are required as a minimum for PK parameters to be summarized. Two values are presented as a min and max with the other summary statistics as NC.

If one or more values for a given parameter is zero, then no geometric statistics are calculated for that parameter and the results for geometric statistics are set to NA (Not Applicable).

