There was approximately 50%, 70%, and 80% peripheral TIM-3 saturation at Cmin at 100 mg, 300 mg and 900 mg Q3W, respectively. No DLTs were observed for the combination. The highest treatment-related toxicities reported were one Grade 3 event of rash at the 100 mg dose level and one Grade 4 event of hypothyroidism at 900 mg dose level. The reported data indicate a trend for dose-dependent antitumor activity with one PR observed for the combination at a TSR-022 dose of 100 mg and 3 PRs at a dose of 300 mg. No efficacy data has been provided for the highest dose level. Part 2 expansion cohorts included patients treated at the same 3 dose levels of TSR-022 in combination with TSR-042 administered at 500 mg (100 mg, n=41; 300 mg, n=110; 900 mg, n=22), both agents administered on a Q3W schedule. For the overall cohort, the rate of patients with treatment-related Grade 3 AEs at each dose level was below 10% (9.2%, 8.2%, 0%), observed AEs consisted predominantly of rash, including 1 participant with Grade 4 lipase increase and 2 participants with immune-related AEs of hypothyroidism and pancreatitis.

Most recently, clinical safety data have been disclosed regarding the PD-L1/TIM-3 bispecific antibody LY3415244. The Phase I study evaluating safety and efficacy of this molecule in participants with advanced cancer was terminated early during the escalation phase due to significant immunogenicity to both arms of the molecule leading to loss of target engagement. In addition, 2 out of 12 participants with high ADA levels developed hypersensitivity reactions (Hellmann et al, 2021).

No clinical safety data have been disclosed regarding the bispecific antibody RG7769. However, based on information in the public domain the compound has completed dose escalation and the RP2D has been set to 2100 mg Q2W.

Overall, the reported AEs of anti-TIM-3 in combination with PD-1 targeting agents indicate that the safety profile is consistent with what has been shown for other PD-1 checkpoint targeting inhibitors and similar across tumor types.

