Appendix C PK Parameter Derivation

Pharmacokinetic parameter definitions and derivations are described in the table below. The following PK Parameters are calculated and summarized for Cycle 1 Day1 and for China population with intensive PK sample collected:

	Derivation	
Area under serum concentration- time curve from time 0 to the last quantifiable concentration	Using the linear up/log down trapezoidal rule	
Area under serum concentration- time curve from time 0 to infinity	Calculated by AUC and then extrapolated by Clast/λz to infinity	
Maximum observed concentration		
Observed lowest concentration before the next dose is administered		
Time to reach maximum observed concentration		
Terminal elimination half-lide	ln 2/λz	
Total body clearance	Dose/AUCinf	
Volume of distribution at steady state	MRT x CL	
Volume of distribution based on the terminal phase	CL/\(\lambda\)z	
Dose normalized AUClast	AUClast/Dose	
Dose normalized AUCinf	AUCinf/Dose	
Dose normalized Cmax	Cmax/Dose	
Dose normalized Ctrough	Ctrough/Dose	
	time curve from time 0 to the last quantifiable concentration Area under serum concentration- time curve from time 0 to infinity Maximum observed concentration Observed lowest concentration before the next dose is administered Time to reach maximum observed concentration Terminal elimination half-lide Total body clearance Volume of distribution at steady state Volume of distribution based on the terminal phase Dose normalized AUClast Dose normalized AUCinf Dose normalized Cmax	

Where appropriate, additional parameters may be calculated.

For Cycle 3, Day 1 (dose escalation) and Cycle 4, Day 1 (dose expansion), both Cmax and Ctrough will be determined as described in the table above.

In addition, the following diagnostic PK Parameters are calculated and summarized for Cycle 1 Day1 and for China population with intensive PK sample collected:

Parameter Symbol (used in CSP/SAP/ CSR)	Definition	Derivation
AUCextr	Extrapolated area under the curve from tlast to infinity, expressed as percentage of AUCinf	
λz	Terminal elimination rate constant	Estimated from linear regression of the terminal part of the log concentration versus time curve
λz lower	Lower (earlier) time used for λz determination	
λz upper	Upper (later) time used for λz determination	
λzN	Number of data points used for λz determination	
λz span ratio	Time period over which λz was determined as ratio of t½λz	λz period (ie, λz upper- λz lower) /t½λz

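### SAP 4.3.2 gives Ctrough no below-LLOQ rule of its own: Cycle 1 trough summaries exclude the lowest troughs, and the later-cycle treatment depends on a sample the SAP does not name

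*SAP*

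**What the plan says.** **NCA rule (SAP 4.3.2).** In each PK sampling period, an NQ concentration "from the time of pre-dose sampling (t=0) up to the time of the first quantifiable concentration is set to a value of zero". For later values: "After this time point, NQ serum concentrations are set to missing for all concentration profiles".

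**Source of Ctrough (SAP 4.3.2).** "Cmax, Crough, tmax, and tlast are taken directly from the concentration-time profiles" (the second item is evidently Ctrough). Appendix C defines it as "Observed lowest concentration before the next dose is administered" and requires it for Cycle 1, and also for C3D1 in dose escalation and C4D1 in dose expansion. It names no sample and gives no NQ rule.

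**Effect of a zero (SAP 4.3.2).** "If one or more values for a given parameter is zero, then no geometric statistics are calculated for that parameter". The other Ctrough statistics (n, arithmetic mean, standard deviation, median, minimum, maximum) are still presented.

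**Concentration table (SAP 4.3.1).** "At a time point where less than or equal to 50% of the concentration values are NQ, all NQ values are set to the LLOQ". Above 50%, but short of all, the geometric mean and gCV are reported as not calculable. The number of values below LLOQ is shown at each time point, and individual NQ results are listed.

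**The concern.** A trough is removed from the Cycle 1 parameter summary because it is low. That is informative exclusion: what remains describes only participants who still had measurable drug at the end of the interval. Appendix C speaks of the lowest observed value, so a programmer could also fall back on the earlier, normally higher, C1D15 sample. That again pushes the summary upward.

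The protocol reasons about exposure at trough. Protocol 4.3.2 predicts receptor occupancy at steady-state Cmin, and Protocol 4.3.3 quotes comparator TIM-3 saturation at Cmin. Protocol 6.6.5 expects the PK data to show adequate exposure and target binding, and PK is one input to the OBD and RP2D. The protocol also recognises that exposure can be lost: it lists anti-drug antibody formation as a potential risk (2.3.1) and describes a PD-L1/TIM-3 bispecific stopped early for "significant immunogenicity to both arms of the molecule leading to loss of target engagement" (4.3.3). At stake is a trough summary that looks better than the data when some participants have lost exposure.

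**Working it through.** The plan states no figure on this point, so there is nothing to reproduce. The check applies each rule to the scheduled samples and then sizes the effect.

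**1. Cycle 1.** Part A PK samples (Protocol Table 2) are C1D1 pre-dose, end of infusion, 4 h and 48 h, then C1D8, C1D15 and C2D1 pre-dose. Part B outside China (Protocol Table 3) has C1D1 pre-dose and end of infusion, C1D8, C1D15 and C2D1 pre-dose. The trough that closes Cycle 1 is C2D1 pre-dose. It follows quantifiable samples, so an NQ value is set to missing.

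**2. C3D1 or C4D1, two readings of Appendix C.**
- *Ctrough is that visit's pre-dose sample.* It is the t=0 value of the period, so NQ becomes 0 and the geometric mean and gCV become not applicable.
- *Ctrough is the sample that closes the interval.* For Part A Cycle 3 this is C4D1 pre-dose; NQ becomes missing and the Cycle 1 bias recurs. Part B has no C5D1 PK sample, which favours the first reading there, but the SAP does not say so.

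**3. Same sample, different results.**

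| Where | NQ trough becomes |
|---|---|
| Parameter table, Cycle 1 | missing |
| Parameter table, C3D1/C4D1, pre-dose reading | 0 |
| Parameter table, C3D1, end-of-interval reading (Part A) | missing |
| Concentration table, 50% or fewer NQ | LLOQ |
| Concentration table, more than 50% NQ | geometric mean and gCV not calculable |

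**4. Size of the Cycle 1 bias.** Let G be the geometric mean of the n−k quantifiable troughs.
- NQ dropped: G.
- NQ = LLOQ: G^((n−k)/n) × LLOQ^(k/n).
- Ratio: (G/LLOQ)^(k/n), for k/n up to 0.5.

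Neither the LLOQ nor any trough is in the documents, so G/LLOQ of 100 to 1000 and the NQ counts are assumptions. The largest planned mTPI-2 cohort is 12 (SAP 3.3.7).
- 1 of 12: 100^(1/12) = 1.47; 1000^(1/12) = 1.78.
- 3 of 12: 100^(3/12) = 3.16; 1000^(3/12) = 5.62.
- 1 of 6: 100^(1/6) = 2.15; 1000^(1/6) = 3.16.

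**5. Illustration (assumed values).** LLOQ = 1; troughs 40, 50, 60, 70, 80 and one NQ.

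| Rule | n | Geometric mean | Mean | Median |
|---|---|---|---|---|
| NQ = LLOQ | 6 | 29.6 | 50.2 | 55 |
| NQ missing | 5 | 58.3 | 60.0 | 60 |
| NQ = 0 | 6 | not applicable | 50.0 | 55 |

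The ratio 58.3/29.6 = 1.97 agrees with 58.3^(1/6). The zero leaves the mean and median essentially where the LLOQ rule puts them.

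**6. Chance that a zero removes the geometric statistics.** 1 − (1−p)^n. With an assumed NQ rate p of 5%, this is 26% at n = 6 and 46% at n = 12; with 2%, 11% and 22%.

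**7. Would an NQ trough mean anything?** The protocol's summary of changes gives a mean half-life of about 10 to 11 days. Over a 21-day interval, 0.5^(21/10) = 0.23 and 0.5^(21/11) = 0.27 of the drug would remain on simple exponential decay. An NQ trough at the higher doses would therefore point to abnormal loss.

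**The case against.** The strongest counter-argument is that the information survives elsewhere. The concentration table covers the same pre-dose samples, applies the LLOQ rule and counts values below LLOQ. NQ results are listed individually, and a dropped participant shows as a smaller n in the parameter table. This stands: a reader might infer that loss of exposure is concealed, and the documents do not support that.

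A reader might also infer that Ctrough is overstated or lost at every cycle. It is not. At C3D1/C4D1, under the pre-dose reading, only the geometric mean and gCV go, and a minimum of 0 would reveal the case. The zero itself depends on a reading that Appendix C leaves open.

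The 4.3.2 text does not expressly say that Ctrough is taken after NQ substitution. But the substitution covers all concentration profiles, Ctrough is read from those profiles, and no exception is given, so this is the natural implementation.

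The effect on decisions is limited. The protocol's named PK parameters are Cmax, AUC, clearance and half-life (Protocol Table 6), although that list is introduced as non-exhaustive and the SAP commits to Ctrough. RP2D selection uses the totality of data (Protocol 6.6.5). ADA effects on PK are analysed outside this SAP (SAP 4.4). Single-participant dose levels are only listed (SAP 3.3.1). The Ctrough/D figures are optional and planned only for C3D1/C4D1 (SAP 4.3.3). The fold-changes rest wholly on assumed values. All of this limits the consequence; none of it reconciles 4.3.1 with 4.3.2.

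**Conclusion.** The point holds for Cycle 1. Followed as written, SAP 4.3.2 excludes NQ troughs from the Cycle 1 Ctrough and Ctrough/D summaries and biases them upward. The geometric mean is inflated by (G/LLOQ)^(k/n) against the SAP's own LLOQ rule: 1.5- to 1.8-fold for 1 of 12 and 3.2- to 5.6-fold for 3 of 12, if G is 100 to 1000 times LLOQ. Those inputs are assumptions; the direction of the bias is not.

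For C3D1/C4D1 the conclusion is conditional. If Ctrough is the visit's pre-dose sample, one NQ value removes the geometric mean and gCV and nothing else. If it is the end-of-interval sample, the Cycle 1 bias recurs. The defect common to both is that the SAP neither names the sample nor gives it an NQ rule. This is a reporting flaw in a secondary PK summary. It is worth correcting before database lock, but it does not threaten the primary endpoints.

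**What to change.** In SAP 4.3.2 and Appendix C:

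1. Name the sample that defines Ctrough for each cycle reported.
2. State that the zero and missing substitutions in 4.3.2 do not apply to Ctrough or Ctrough/D. These follow 4.3.1: LLOQ when 50% or fewer are NQ; geometric mean and gCV not calculable when more than 50% are NQ.
3. Show the number of NQ troughs beside the Ctrough statistics.

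The cost is a short SAP edit, with no new data and no change to study conduct. There are two drawbacks. LLOQ is an upper bound for an NQ trough, so some overstatement remains. LLOQ/Dose also falls mechanically as dose rises, so NQ-derived Ctrough/D values should be flagged in the dose-normalised plots.

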4.3.3 Graphical presentation of Pharmacokinetic Concentration and Parameter Data

All mean (arithmetic mean and/or gmean) plots or combined plots showing all participants by treatment are based on the PK analysis set. Individual plots by participant are based on the safety analysis set.

For consistency, the serum concentration values used in the mean (arithmetic mean and/or gmean) data graphs are those given in the descriptive statistics summary table for each time point.

For gmean concentration-time plots, NQ values are handled as described for the descriptive statistics; if the geometric mean is NQ, the value plotted is zero for linear plots and missing for semi-logarithmic plots. Any gmean±gSD error bar values that are negative are truncated at zero on linear concentration-time plots and omitted from semi-logarithmic plots.

For individual plots, serum concentrations which are NQ prior to the first quantifiable concentration are set to a value of zero (linear plots only). After the first quantifiable concentration, any NQ serum concentrations are regarded as missing.

Data permitting, the following figures may be presented as appropriate:

- Figures for the gmean serum concentration-time data (with ±gSD error bars) presented on both linear and semi-logarithmic scales using scheduled post-dose time as follows:
 - By PK Day with all dose level/cohort overlaid on the same plot
- Individual participant serum concentration-time data graphically presented on both linear and semi-logarithmic scales using actual time post-dose as:
 - Combined individual plots by dose level/cohort with all participants overlaid on the same plot for each dose level/cohort
- Box-plot of pharmacokinetic parameters versus dose level/cohort:
 - Cmax/D, AUCinf/D and AUClast/D at C1D1
 - Cmax/D and Ctrough/D at C3D1 (dose escalation) or C4D1 (dose expansion)
- Individual and geometric mean of dose normalized pharmacokinetic parameters versus dose level/cohort:
 - Cmax/D, AUCinf/D and AUClast/D at C1D1
 - Cmax/D and Ctrough/D at C3D1 (dose escalation) or C4D1 (dose expansion)

4.3.4 Precision and Rounding Rules for Pharmacokinetic Concentration and Parameter Data

PK concentration data

PK concentration data listings present to the same number of significant figures as the data received from the bioanalytical laboratory (usually but not always to 3 significant figures) and against the same units as received.

PK concentration descriptive statistics present 4 significant figures with the exception of the min and max which present 3 significant figures and n and n<LLOQ which present as integers.

PK parameter data

PK parameter listings are presented according to the following rules:

- Cmax, Ctrough, Cmax/D and Ctrough/D: present to the same number of significant figures as received from the bioanalytical laboratory
- tmax, tlast, λz lower and λz upper: present as received in the data, usually to 2 decimal places
- AUCinf, AUClast, AUCinf/D, AUClast/D, AUCextr, λz, t½λz, CL, Vss, Vz, Rsq, Rsq adj, λz span ratio: present to 3 significant figures
- λzN: present as an integer (no decimals)

The descriptive statistics for PK parameter data are presented to 4 significant figures with the exception of the min and max which are presented to 3 significant figures apart from the following:

- tmax, and tlast: present as received in the data, usually to 2 decimal places
- number of values (n): present as an integer

